#### 8.2 Handling of Missing Data

Missing data will be imputed using the following methods for the effectiveness analyses:

- Multiple Imputation (MI): If there are any mITT participants with missing ATHS score at Month 6 on either side of temple, MI by the Fully Conditional Specification (FCS) method will be used to impute the missing data in ordinal scale by treatment group and by side of temple (left and right). Details of the MI method for primary analysis are provided in Section 8.3.2.
- Non-Responder Imputation (NRI): For sensitivity analysis, the NRI method will categorize any participants with missing Month 6 ATHS scores as non-responders.
- As Observed (AO): The AO method will analyze the data based on the observed values without imputation for the missing values. Thus, a participant who does not have an evaluation on a scheduled visit will be excluded from the AO analysis for that visit. The AO method will be used for sensitivity analysis of primary effectiveness endpoint using the OPE population.

#### 8.3 Primary Effectiveness Endpoint(s) and Analyses

#### 8.3.1 Primary Effectiveness Endpoint(s)

The primary effectiveness endpoint is the ATHS responder status at Month 6 in CP based on EI's assessment. A responder is defined as a participant with at least 1-grade

improvement (reduction) from baseline on the ATHS (described in Table 5) on both temples.

#### Table 5.Allergan Temple Hollowing Scale

Score	Grade	Description
0	Convex	Rounded temple
1	Flat	Flat temple; temporal fusion line may be visible
2	Minimal	Shallow depression or concavity with minimal volume loss; temporal fusion line may be visible
3	Moderate	Moderate depression or concavity with moderate volume loss; moderate prominence of temporal fusion line
4	Severe	Deeply recessed, sunken appearance; marked prominence of temporal fusion line and zygomatic arch

#### 8.3.2 Handling of Missing Data for the Primary Effectiveness Endpoint(s)

If there are any mITT participants with missing scores for the primary effectiveness endpoint, the following missing-data handling method is planned.

Step 1: The missing data will be imputed by treatment group and by side of the temple using the FCS method for ordinal data (via SAS procedure MI with FCS logistic statement). Thirty (30) imputed datasets will be generated, using *seed* = 1878701 and *nimpute* = 30 based on the following model:

Month 6 ATHS =  $\beta_0 + \beta_1 \times \text{Baseline ATHS} + \beta_2 \times \text{Month 1 ATHS} + \beta_3 \times \text{Month 3 ATHS}$ 

Step 2: With the FCS logistic statement in the MI procedure, each imputed dataset will have ATHS scores of 0, 1, 2, 3, or 4. After imputation, the changes from baseline will be calculated, from which the responder status in ATHS at Month 6 of CP will be determined. Intermittent missing ATHS at Month 1 and Month 3 will be imputed by similar models using ATHS at previous visits as covariates.

Step 3: Each complete (imputed) dataset obtained from Steps 1 and 2 will be analyzed using SAS procedure FREQ.

Step 4: The pooled results will be obtained using PROC MIANALYZE.

The aggregated responder rates by treatment group and the associated p-value and 95% CI will be presented to assess the difference in the ATHS responder rate at Month 6 of CP between VOLUMA and the no-treatment control. If the 2-sided p-value is  $\leq 0.05$ , then the ATHS responder rate at Month 6 in VOLUMA XC is statistically significantly different from that in the no-treatment control group.

#### 8.3.3 Primary Effectiveness Analysis

Primary effectiveness analysis will be performed based on the mITT population. The study intervention will be determined to be clinically effective if the following criterion is met:

• The ATHS responder rate for the treatment group is statistically superior to the responder rate for the control group at Month 6

The null and alternate hypotheses are:

$$H_o: P_v = P_c \text{ versus } H_a: P_v \neq P_c$$

where  $P_v$  and  $P_c$  denote the responder rates for the treatment group at Month 6 after the latest of randomization, initial treatment and touch-up treatment, and control group at Month 6 after randomization, respectively.

#### 8.3.4 Additional Analyses of the Primary Effectiveness Endpoint(s)

If there are any mITT participants with missing scores for the primary effectiveness endpoint, then a sensitivity analysis of the primary effectiveness endpoint will be performed for the OPE population using the Fisher's exact test for group comparison.

A second sensitivity analysis of the primary effectiveness endpoint will also be performed using Fisher's exact test for the mITT population with missing ATHS responder status at Month 6 imputed as non-responders.

The primary analysis using Fisher's exact test will also be performed for the PP population based on AO method for the missing data imputation as a third sensitivity analysis.

#### 8.4 Secondary Effectiveness Analyses

There are 4 secondary effectiveness measures, to be recorded at the participant level rather than for each temple. The secondary effectiveness endpoints include:

- Responder status for EI assessment of GAIS (described in Table 6) in the temple area at Month 6 during CP
- Responder status for participant assessment of GAIS in the temple area at Month 6 during CP
- Change from baseline in participant responses to FACE-O Satisfaction with Facial Appearance questionnaire, for the Rasch-transformed score (0 - 100) at Month 6 during CP
- Change from baseline in participant responses to FACE-Q Satisfaction with Temples questionnaire, for the Rasch-transformed score (0 - 100) at Month 6 during CP

A GAIS responder for EI assessment is defined as a participant who shows improvement in the overall aesthetic assessment (Improved or Much Improved on GAIS) based on EI assessment in the temple area at the Month 6 visit.

A GAIS responder for participant assessment is defined as a participant who shows improvement in the overall aesthetic assessment (Improved or Much Improved on GAIS) based on participant assessment in the temple area at the Month 6 visit.

For the responder status based on the EI's and participant's assessments of GAIS at Month 6, the responder rates with 95% exact CI will be summarized, and p-value for

between treatment group comparisons will be based on 2-sided Fisher's exact test using observed data.

Grade	Description
Much Improved	Marked improvement in appearance
Improved	Improvement in appearance, but a touch-up or retreatment is indicated
No Change	The appearance is essentially the same as the original condition
Worse	The appearance is worse than the original condition
Much Worse	The appearance is much worse than the original condition

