#### 9.4.1. General Considerations

The effectiveness analyses will be based on the mITT population in general, and PP sensitivity analysis of the primary endpoint will be based on the PP population. Baseline for effectiveness is defined as the last nonmissing effectiveness assessment before randomization.

All statistical tests will be 2-sided hypothesis tests performed at the 5% level of significance for main effects. A gatekeeping procedure will be used for hypothesis testing of the primary endpoint (ATHS responder) and 2 of the secondary endpoints (responder rates for EI and participant assessments of GAIS) following a predefined sequence to control the overall type I error rate at the 0.05 level. The primary hypothesis must be rejected in order to test the responder rate for EI assessment of GAIS. Additionally, statistical significance must be established for the responder rate for EI assessment of GAIS in order to assess the hypothesis for the responder rate for participant assessment of GAIS.

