### 9.4.2.3. Sensitivity Analyses

Since multiple imputation will be used for the primary analysis if the observed dataset is not complete for the primary endpoint, a sensitivity analysis will then be done using observed data, without imputation of missing data.

If so, a second sensitivity analysis will be done after imputation for missing data by baselineobservation carried-forward (for reversion to baseline), which effectively handles participants with missing primary effectiveness as nonresponders.

The primary analysis using 2-sided Fisher's exact test or multiple imputation (depending on whether any participants have missing primary effectiveness endpoint as mentioned in Section 9.4.2.2) will also be repeated on the PP population as a third sensitivity analysis.

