#### 9.4.3. Secondary Endpoints

Secondary effectiveness endpoints:

- Responder status based on the EI's assessment of the temple area using GAIS at Month 6 after last treatment for treatment group and after randomization for control group, where a "responder" is a participant with grade "improved" or "much improved" on GAIS.
- Responder status based on the participant's assessment of the temple area using GAIS at Month 6 after last treatment for treatment group and after randomization for control group, where a "responder" is a participant with grade "improved" or "much improved" on GAIS.
- Change from baseline on FACE-Q Satisfaction with Facial Appearance questionnaire at Month 6 after last treatment for treatment group and after randomization for control group.
- Change from baseline on FACE-Q Satisfaction with Temples questionnaire at Month 6 after last treatment for treatment group and after randomization for control group.

The following analysis will be performed for the secondary effectiveness endpoints:

- For the responder status based on the EI's and participant's assessments of GAIS at Month 6, the responder rates with 95% exact CI will be summarized, and p-value for between treatment group comparisons will be based on 2-sided Fisher's exact test using observed data.
- Change from baseline on participant responses on FACE-Q Satisfaction with Facial Appearance and with Temples questionnaires, for the Rasch-transformed score (0-100), will be analyzed using a repeated measures mixed-effects model, and the p-value for the between treatment group comparison will be provided for Month 6.

CONFIDENTIAL JUVÉDERM® VOLUMA® with Lidocaine injectable gel

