#### Table 6.Global Aesthetic Improvement Scale

The other secondary effectiveness measures are the participant responses on the FACE-Q questionnaires: Satisfaction with Facial Appearance and Satisfaction with Temples.

Change from baseline on participant responses on FACE-Q Satisfaction with Facial Appearance and with Temples questionnaires, for the Rasch-transformed score (0-100) will be analyzed using a mixed-effects model for repeated measures, and the nominal p-value for the between treatment group comparison will be provided for Month 6.

For FACE-Q Satisfaction with Facial Appearance questionnaire and FACE-Q Satisfaction with Temples questionnaire, the responses to all the items will be summed and converted to a Rasch-transformed score that ranges from 0 to 100 (higher score indicates increased satisfaction) using the algorithm developed by the FACE-Q scale developers.

For items with missing data (which includes selection of more than 1 response for an item, a response of non-applicable (N/A) or skipping a question), insert the unrounded mean of the completed items into the total sum score. The summed score including the imputation of missing items is rounded to the nearest integer and converted to the Rasch transformed score using the conversion table below. Higher scores reflect a better outcome. The converted score ranges from 0 (worst) to 100 (best). If less than 50% of the questions have been answered, then the overall score will be missing.

The secondary effectiveness endpoints will be analyzed based on mITT population based on the observed data.

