# 12.0 Overall Type-I Error Control

All statistical tests will be 2-sided hypothesis tests performed at the 5% level of significance for main effects. A gatekeeping procedure will be used for hypothesis testing of the primary endpoint (ATHS responder) and 2 of the secondary endpoints (responder rates for EI and participant assessments of GAIS) following a predefined sequence to control the overall type I error rate at the 0.05 level. The primary hypothesis must be rejected in order to test the responder rate for EI assessment of GAIS. Additionally, statistical significance must be established for the responder rate for EI assessment of GAIS in order to assess the hypothesis for the responder rate for participant assessment of GAIS.

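### Do the two gated GAIS responder tests need a planned missing-data sensitivity analysis because they use observed Month 6 data only?

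*SAP*

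**What the plan says.** Protocol 9.4.3 sets the GAIS analysis: "p-value for between treatment group comparisons will be based on 2-sided Fisher's exact test using observed data". SAP 8.4 repeats it ("between treatment group comparisons will be based on 2-sided Fisher's exact test using observed data"), and closes the section with a general rule for all four secondary endpoints: "The secondary effectiveness endpoints will be analyzed based on mITT population based on the observed data".

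Both GAIS endpoints sit inside the error-controlled sequence. SAP 12.0 says "A gatekeeping procedure will be used for hypothesis testing of the primary endpoint (ATHS responder) and 2 of the secondary endpoints", and Protocol 9.4.1 gives the order: "The primary hypothesis must be rejected in order to test the responder rate for EI assessment of GAIS", with participant GAIS following EI GAIS. The two FACE-Q endpoints are outside the sequence and receive a nominal p-value.

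The missing-data methods are confined to the primary endpoint. SAP 8.2 limits multiple imputation to Month 6 ATHS, and of non-responder imputation it says: "For sensitivity analysis, the NRI method will categorize any participants with missing Month 6 ATHS scores as non-responders". SAP 8.3.4 lists observed-data, non-responder and per-protocol checks, all for ATHS; the non-responder one begins "A second sensitivity analysis of the primary effectiveness endpoint will also be performed using Fisher's exact test for the mITT population". Protocol 9.4.2.3 plans the same check by carrying baseline forward, "which effectively handles participants with missing primary effectiveness as nonresponders". Protocol Section 9 states openly that imputation is reserved for the primary effectiveness analyses. SAP Appendix C adds nothing for GAIS.

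**The concern.** A result declared under overall type I error control carries more weight than a descriptive one, and a reader will ask whether it survives the missing data. Protocol 9.2 allows for 20% loss between randomization and Month 6, which is about 33 of 168 participants. For ATHS the sponsor planned imputation plus three sensitivity analyses. For GAIS, measured at the same visits with the same exposure to loss, it planned none.

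The design also gives reasons why loss might differ between arms. Participants know their allocation, controls are offered treatment on the day of their Month 6 visit, and treated participants who have a touch-up reach Month 6 about a month later after randomization than controls do. If loss were unequal and related to outcome, a GAIS claim could depend on who was left out, and any check would be chosen after the data had been seen.

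**Working it through.** **Inputs.** From Protocol 9.2 and SAP 2.4: 112 and 56 randomized, 90 and 45 evaluable, 20% loss, two-sided Fisher's exact test at 5%, ATHS responder rates 65% and 35%. Neither document gives a GAIS rate, so every GAIS rate below is an assumption.

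**The plan's own figure.** Summing the Fisher rejection probability over Binomial(90, 0.65) and Binomial(45, 0.35) gives 90.8% power, which agrees with the stated minimum of 90%. Loss of 20% leaves 112 × 0.8 = 89.6 and 56 × 0.8 = 44.8, in line with 90 and 45.

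**Method.** Test the observed table, then count all missing participants as non-responders over 112 and 56, and compare.

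**Equal loss**

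| Loss | Observed | p, observed | p, missing = non-responder |
|---|---|---|---|
| 20% | 72/90 vs 16/45 | <0.0001 | <0.0001 |
| 20% | 58/90 vs 16/45 | 0.0018 | 0.0051 |
| 10% | 66/101 vs 18/50 | 0.0009 | 0.0018 |
| 20%, edge case | 49/90 vs 16/45 | 0.045 | 0.066 |

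The last row is the smallest treated count that is significant against 16/45 (48/90 gives 0.067).

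**Lower control rates.** The 35% is described in Protocol 9.2 as an upper limit and rests partly on the ATHS validation results. GAIS is a different measure: a comparison with baseline photographs, made by the EI and separately by participants who know whether they were treated. So lower control rates belong in the range. At 20% equal loss, taking the smallest significant treated count each time:

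| Control | Treated | p, observed | p, missing = non-responder |
|---|---|---|---|
| 0/45 | 9/90 | 0.029 | 0.030 |
| 2/45 | 16/90 | 0.034 | 0.036 |
| 4/45 | 22/90 | 0.037 | 0.041 |
| 9/45 | 34/90 | 0.0495 | 0.060 |

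In the first three rows even the most borderline result holds. At 9/45 it flips.

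**How often the two tests disagree.** This is the exact binomial probability that the observed test favours treatment at p ≤ 0.05 and the non-responder version does not, under equal random loss:

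| True rates | Loss | Disagreement |
|---|---|---|
| 65% / 35% | 20% | 3.7% |
| 55% / 35% | 20% | 5.3% |
| 80% / 35% | 20% | 0.12% |
| 55% / 20% | 20% | 0.6% |
| 65% / 20% | 20% | 0.04% |
| 50% / 10% | 20% | 0.03% |
| 65% / 35% | 10% | 0.04% |

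Under random loss the observed-data test is valid. These figures therefore measure the power given up by scoring missing as failure; they do not measure bias in the planned test.

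**What it takes to keep a flipped claim**
- Edge case: let 4 of the 11 missing controls respond, about their observed rate, so control is 20/56. The claim stands if 10 of the 22 missing treated respond (59/112, p=0.049) and fails with 9 (58/112, p=0.051). Ten of 22 is 45%, against 49/90 = 54% observed.
- Assumed unequal loss of 30 treated and 3 controls: 53/82 vs 19/53 gives p=0.0014, and 53/112 vs 19/56 gives p=0.14. Four of the 30 missing treated responding (13%, against 53/82 = 65% observed) restores p=0.048. If one of the 3 missing controls also responds, 6 of 30 (20%) suffice (59/112 vs 20/56, p=0.049).
- Loss the other way, 18 treated and 15 controls: 61/94 vs 14/41, p=0.0013, becomes 61/112 vs 14/56, p=0.0003. Counting missing as non-response is then the less cautious analysis.

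**The case for a change.** The strongest case for a change is that the omission is real and cheap to fill. One extra Fisher test and one imputation run per endpoint would use data already collected, leave the gated tests, alpha and sample size alone, and settle the check in advance for two claims that the sponsor chose to place under error control. Participants are unblinded and controls have a reason to stay until Month 6, so unequal loss cannot be dismissed. The replacement rule in Protocol 9.2, which enrols more participants if over 20% miss the in-clinic ATHS, protects numbers and not against bias. Multiple imputation could not be rebuilt from summary tables.

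All of that is true, but it does not show that the plan as written gives a wrong or worse answer. The proposal would keep the observed-data test as the deciding one. The non-responder check leaves no discretion to an analyst: it is one fixed table per endpoint, and the counts follow from outputs already planned (population sizes in SAP 4.0, GAIS responder counts in Table 7). Imputation would assume missing at random, and non-responder scoring can favour the device when controls are lost more often, so neither addresses the unequal, informative loss that motivates the worry. EI GAIS should be missing largely where ATHS is missing, and there the imputed, observed, non-responder and per-protocol ATHS results will already show how sensitive the trial is to loss. Participant GAIS may be less exposed, because Protocol 8.1.4 allows questionnaires to be supplied for remote completion.

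What stands is that a formal sensitivity result for GAIS would be supportive information of modest value if loss is heavy.

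**Conclusion.** No change is needed. Testing GAIS on observed data is a stated and consistent choice, prespecified in both documents, and a fair trade-off for secondary endpoints. It is valid if missingness is unrelated to outcome within arm, and it leaves the ATHS effectiveness conclusion untouched (Protocol 9.4.2.2, SAP 8.3.3).

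The possible impact is narrow. A flip needs either a borderline effect with a control response rate towards the ATHS upper limit (present at 9/45 and 16/45, absent at 0, 2 and 4 of 45) at about 20% loss, or strongly unequal loss such as 30 against 3, which nothing in the documents predicts. Even then, missing treated participants must respond less often than those observed for the claim to be lost: fewer than 45% against 54% in the edge case, and fewer than 13% to 20% against 65% in the unequal case.

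This rests on assumed GAIS rates. If actual Month 6 loss proves high or clearly unequal, the GAIS results should be read beside the missing counts by arm, which the planned outputs allow.

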#### Table 6.Global Aesthetic Improvement Scale

The other secondary effectiveness measures are the participant responses on the FACE-Q questionnaires: Satisfaction with Facial Appearance and Satisfaction with Temples.

Change from baseline on participant responses on FACE-Q Satisfaction with Facial Appearance and with Temples questionnaires, for the Rasch-transformed score (0-100) will be analyzed using a mixed-effects model for repeated measures, and the nominal p-value for the between treatment group comparison will be provided for Month 6.

For FACE-Q Satisfaction with Facial Appearance questionnaire and FACE-Q Satisfaction with Temples questionnaire, the responses to all the items will be summed and converted to a Rasch-transformed score that ranges from 0 to 100 (higher score indicates increased satisfaction) using the algorithm developed by the FACE-Q scale developers.

For items with missing data (which includes selection of more than 1 response for an item, a response of non-applicable (N/A) or skipping a question), insert the unrounded mean of the completed items into the total sum score. The summed score including the imputation of missing items is rounded to the nearest integer and converted to the Rasch transformed score using the conversion table below. Higher scores reflect a better outcome. The converted score ranges from 0 (worst) to 100 (best). If less than 50% of the questions have been answered, then the overall score will be missing.

The secondary effectiveness endpoints will be analyzed based on mITT population based on the observed data.

#### 8.5 Additional Effectiveness Analyses

The other effectiveness analyses will be performed for all variables listed in Table 7. Analyses on the primary and secondary variables at other visits will be performed. All analyses are based on observed data and missing data will not be imputed. All analyses are performed by treatment group and by visit. Additionally, no hypothesis will be tested and, thus, no multiplicity adjustment will be performed.

For CP, the mITT population will be used, including Month 1, 3 and 6 visits.

For TP of the VOLUMA group, the VIT population will be used, including Month 1, 3, 6, 9 and 12 visits.

For TP of the control group, the VOT population will be used, including Month 1, 3 and 6 visits.

In the responder analysis on FACE-Q Satisfaction with Facial Appearance and Satisfaction with Temples questionnaires, a responder is defined as any participant whose postbaseline Rasch-transformed score is greater than their baseline Rasch-transformed score.

For the descriptive summary of ATHS overall score, the temple with worse baseline score will be used to represent the participant; if both temples have he same baseline score, the left side temple will be used to represent the participant.

For participant's self-perception of age in treatment group, change from baseline (e.g., -10 ="I look 10 years younger," 0 ="I look my age," and +6 ="I look 6 years older") will be calculated and summarized descriptively. The paired t-test nominal p-value will be calculated at Month 6 as descriptive guidance to consider if the change from baseline is different from zero for the primary timepoint of Month 6.

